## 2.2 Purpose of the Study

This study is part of the global clinical assessment program of *IQOS* which is designed to provide scientific evidence to further substantiate the potential of reduced risk of using *IQOS* as compared to smoking cigarettes. The main goals of this exploratory study are to assess whether switching from cigarette smoking to using *IQOS* will influence 1) VO2max and exercise capacity, 2) ability to perform exercise training and thereby influence 3) VO2max after 12 weeks of exercise training, 4) physiological parameters and biological health markers, and finally 5) physical activity levels in daily life.

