# 4 INVESTIGATIONAL PLAN

## 4.1 Overall Study Design and Plan

This is a randomized, controlled, open-label, 4-arm parallel group study with stratification by daily cigarette consumption over the last 12 months prior to V1 as reported during V1 (i.e., 10 to 19 cigarettes or >19 cigarettes per day) and sex (Figure 2).

A sufficient number of healthy adult smokers will be screened and enrolled after checking that all eligibility criteria have been met, in order to reach 90 randomized subjects.

Smokers will be randomized as follows with a 5:5:5:3 ratio according to strata:

- 1. switch to IQOS use + participation in training program: IQOS-1 arm, 25 subjects
- 2. continue cigarette smoking + participation in training program: Cigarette arm, 25 subjects
- 3. smoking abstinence + participation in training program: SA arm, 25 subjects
- 4. switch to *IQOS* use only: *IQOS*-2 arm, 15 subjects

When 90 randomized subjects are reached, further enrollment will be stopped. Subjects already enrolled in the study will still be eligible for randomization. From randomization, subjects will be instructed to use their allocated product or stay smoking abstinent until the end of the study. Drop-outs will not be replaced.

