### **Confidentiality Statement**

Philip Morris Products SA	Philip Morris Products SA Clinical Study Protocol	
P1-EXC-01-EU	Version 3.0 / 2 May 2019	Page 42 of 151

Training program, from V5 (15±2 days after V3) until V42 (99±2 days after V3): Subjects randomized into *IQOS*-1, cigarette and SA arms will participate in 38 supervised training sessions during a 12-week period using three different training protocols (Appendix 2).

Subjects randomized to the *IQOS*-2 arm will come for visits once a week for all assessments except the training. Subjects in the *IQOS*-2 arm will consequently only attend the following visits: V5, V7, V9, V14, V16, V19, V23, V28, V30, V33, V35 and V39.

At V14 and V28 (medical visits), safety and biological health marker and exposure marker assessments will be performed for all subjects.

Before each training, the following assessments will be conducted;

- Weight
- Exhaled CO
- 30-60 min before start of the training subjects in cigarette and *IQOS* arms will smoke a cigarette or use a HeatStick, respectively (only if they are willing to).

All trainings will be performed on a bike ergometer. The training intensity will be adjusted according to the subject's resting heart rate as determined by ECG at V3 and maximal heart rate as determined at the VO2max test at V4 (acute test). The work produced, the work rate and heart rate will be recorded for each training (as described in Objective 3).

Between V42 and V43, subjects having signed the optional section of the ICF will have an interview (by phone or computer) on the topic of health and functioning lasting around 60 minutes.

Training effect, V43 (106±2 days after V3):

Before the VO2max test, biological health markers, exposure markers, vital signs, exhaled CO, weight, body-fat percentage and waist circumference measurements will be performed. Then, 30-60 min before start of the VO2max test subjects in cigarette and *IQOS* arms will smoke a cigarette or use a HeatStick, respectively (only if they are willing to). Subjects' VO2max will be determined as described for V3, including determination of lactate levels and perceived exertion rate. After completing the VO2max test, the subject will rest for  $60\pm5$ min, after which the exercise capacity test will be performed. After completing exercise tests, total blood volume will be determined.

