# 4.2 Rationale for Study Design

PMI is now launching a series of new clinical studies to better understand the additional benefits the reduced exposure of *IQOS* can offer to its consumers. Because of the recognized adverse effects of smoking on exercise capacity, this exploratory study is part of the program. The overall objective of the *IQOS* design is to provide an acceptable alternative to cigarettes for current, adult smokers, with substantial reduction of exposure to HPHCs by its aerosol compared to cigarette smoke.

Based on the well-known role of hemoglobin in blood oxygen transport and the formation of COHb upon CO exposure, it is assumed that when cigarette smokers switch to a smoke- and CO-free product, such as *IQOS*, their exercise capacity and response to exercise training will increase as a consequence of normalization of COHb levels and increased blood oxygenation. In order to explore this assumption, and to further assess the role of CO, smokers will be randomized to switching to *IQOS* use (*IQOS-1, IQOS-2*), continuing cigarette smoking and smoking abstinence (SA). In a previous study an effect on VO2max already after 8h of smoking abstinence has been reported (9). In this study the acute effect of switching to *IQOS* will be assessed one week after randomization. In order to assess the impact on the response to exercise training, all subjects besides the *IQOS-2* arm, will participate in a 12-week exercise training program. Whereas a reduced CO exposure in the SA-arm and the *IQOS-1* arm is thought to favorably impact response to training, continued exposure to CO in the cigarette arm would reduce the training effect in sedentary healthy smokers.

The training program designed for this study is based on previous studies demonstrating that in order to achieve improvements in cardiorespiratory fitness the optimal training frequency consists of at least 3 training sessions at a moderate intensity (~65% of maximal workload) per week (43). A bike exercise is recommended as compared to running due to the lower risk of

Data and information contained in this document are considered to constitute trade secrets and confidential commercial information, and the legal protections provided to such trade secrets and confidential information are hereby claimed under the provisions of applicable law. No part of this document may be publicly disclosed without the written consent of Philip Morris Products S.A

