# 9.4.2 Exercise Training Program

 $7\pm1$  days after V4 all subjects besides those who are randomized to the *IQOS*-2 (no training) arm, will start a 12-week exercise training program, from V5 (15±2 days after V3) until V42 (99±2 days after V3).

Subjects will attend trainings sessions 2-4 times per week and three different training programs will be circulated as described in Appendix 2. All trainings will be performed indoor on stationary bikes.

Subjects in the *IQOS*-2 arm will only attend V5, V7, V9, V14, V16, V19, V23, V28, V30, V33, V35 and V39 but not for training sessions.

Table 9 shows the procedures that will be performed at each training from V5 to V42.

Time	Blood Sample	Procedures	Additional Information
Start of Procedure		V5-V42	
Before training		Urine pregnancy test	V5 only
Before training		Weight	
Before training		CO breath test	
30-60 min before the training		Subjects in I QOS-1 and I QOS-2 arms will use a HeatStick. Subjects in cigarette arm will smoke a cigarette	Only subjects willing to
		40-min bike exercise training	As per training program schedule in Appendix 2. The training intensity will be adapted for each subject based on the resting and maximal HR.
		Concomitant medication	
		AE/SAE and device event recording	At any time during the day.

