# 12.5 Endpoint Analysis

To evaluate changes in VO2max in subjects switching to *IQOS*, continuing to smoke cigarettes and being smoking abstinent.

A linear mixed effects model will be used to estimate the difference in VO2max between each arm (SA arm, *IQOS*-1 arm) versus cigarette arm one week after randomization (V4) and after completion of the 12-week training program (V43). The dependent variable will be the VO2max with baseline VO2max, arm, sex, age and baseline cigarette consumption as covariates. Self-reported cigarette consumption and/or *IQOS* use will be added as a covariate as well. Appropriate contrasts will be constructed to report an estimate of the VO2max and its 95% confidence intervals within each arm and also between SA arm, *IQOS*-1 arm vs cigarette arm. The comparison between SA vs *IQOS*-1 arm will be calculated as well.

To estimate the difference in  $VO_2max$  between *IQOS*-2 and other arms, the same model will be used to model the change between arms only at V43.

Other covariates may be added as deemed appropriate. The same analysis will be repeated for weight-adjusted and fat-free weight adjusted VO2max. Estimates of variability from the statistical model will be reported and may be used to power future similar studies.

To evaluate changes in exercise capacity in subjects switching to *IQOS*, continuing to smoke cigarettes and being smoking abstinent

The linear mixed effects model as described above for  $VO_2max$  will be used to estimate the difference in exercise capacity between the *IQOS*-1 or SA arm versus cigarette arm one week after randomization (V4) and after completion of the 12-week training program (V43). The dependent variable will be the time to complete the test in seconds with baseline exercise capacity (in seconds) as a covariate.

Other covariates may be added as deemed appropriate. Estimates of variability from the statistical model will be reported and may be used to power future similar studies.

To assess the intensity of the exercise training in subjects switching to *IQOS*, continuing to smoke cigarettes and being smoking abstinent

An appropriate statistical model will be used to estimate the intensity of exercise training in the various (cigarette, *IQOS*-1 and SA) arms over time. The exercise intensity will be the endpoint with baseline exercise intensity, age, visit, sex and arm as covariates. Self reported

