9.1.3 Definitions for Statistical Data Analysis

The baseline value for any given parameter will be the last assessment prior to randomization for the subjects randomized to either IQOS, cigarette or SA arms.

Change from baseline (i.e. difference of post baseline value compared to baseline value) will be calculated as: Change from baseline = post baseline value – baseline value.

Confidentiality Statement

Philip Morris Products SA.	Statistical Analysis Plan	Confidential
P1-EXC-01-EU	Final 2.0	Page 35 of 71
Related to PMI-RRP-WKI-112487		

For log-transformed variables, the (relative) change from baseline is defined as: Change from baseline = log(post baseline value / baseline value).

For step count, the baseline will be the average steps taken between V2 and V3.

Time variables, i.e. exercise capacity and time spent at different percentages of maximal work rate (or maximal HR) during each training session will be analyzed in seconds (not in min:sec).

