Data and information contained in this document are considered to constitute trade secrets and confidential commercial information, and the legal protections provided to such trade secrets and confidential information are hereby claimed under the provisions of applicable law. No part of this document may be publicly disclosed without the written consent of Philip Morris Products S.A

Philip Morris Products SA.	Statistical Analysis Plan	Confidential
P1-EXC-01-EU	Final 2.0	Page 42 of 71
Related to PMI-RRP-WKI-112487		

will be excluded from this analysis. However, if the workload for all visits (V3, V4 and V43) were wrong but the same then the subject will be included in the analysis.

The comparisons of interest will follow Table 4 and Table 5 with estimates for within and between arms presented together with their 95% confidence intervals. A scatter plot of change in time to complete the test versus maximum work rate by arm will be plotted as well.

Other covariates may be added as deemed appropriate. Estimates of variability (e.g. "Covariance Parameter Estimates") from the statistical model will be reported (at least in the original statistical output listings) and may be used to power future similar studies.

A separate sensitivity analysis with all subjects including those with incorrectly calculated work load will be analyzed as well using the same analysis.

9.6.1.1.3 To assess the intensity of the exercise training in subjects participating in a training program switching to IQOS, continuing to smoke cigarettes and being smoking abstinent

The SAS procedure PROC MIXED will be used with the restricted maximum likelihood method for estimation of the intensity of exercise training in the various (cigarette, IQOS-1 and SA) arms over time. The change from baseline (defined as V5) in exercise intensity will be the endpoint with age, visit, sex, arm, visit*arm, baseline cigarette consumption at V1 and daily cigarette consumption as covariates. Endpoints to be analyzed as exercise intensity are

- Cumulative work produced during each training session (calories and calories/kg body weight)
- Average work rate during each training session (watt and watt/kg body weight)

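### Modelling training work as change from V5, about two weeks after the switch, removes any product effect already present at the first session

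*SAP*

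**What the plan says.** The SAP, 9.6.1.1.3, on cumulative work and average work rate: "The change from baseline (defined as V5) in exercise intensity will be the endpoint". The covariates are age, visit, sex, arm, visit by arm, cigarette consumption at V1 and daily cigarette consumption. There is no V5 level and no pre-randomisation fitness term. Arm comparisons with 95% CIs are named for V14, V28 and V42.

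The protocol, 12.5, has a different form: "The exercise intensity will be the endpoint with baseline exercise intensity, age, visit, sex and arm as covariates". It leaves further detail to the SAP. SAP section 7, on changes from the protocol, mentions only the biochemical-verification analysis.

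On timing, Protocol 4.1 says: "From randomization, subjects will be instructed to use their allocated product or stay smoking abstinent until the end of the study". Protocol 9.4.2 places V5 at 15±2 days after V3.

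On purpose, Protocol 2.2 asks whether switching influences, as its second item, "2) ability to perform exercise training". Objective 3 is to assess the intensity of training. Objectives 1, 2, 4, 7 and 8 are worded in terms of changes; objective 3 is not.

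**The concern.** The product is expected to act early. In Protocol 4.2 an effect on VO2max "already after 8h of smoking abstinence has been reported", and the trial tests its own acute effect about a week after V3. If less carbon monoxide lets subjects do more work at a given heart rate, some of that gain may already be in the V5 session. Subtracting V5 takes it out of every later contrast.

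At stake is what the modelled answer to objective 3 means. An arm that does more work from the first session to the last would be reported, with confidence intervals, as no different from the cigarette arm. A reader of that table would take it as a statement about ability to train.

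**Working it through.** **Inputs.** Allocated use starts at V3; V5 follows 13 to 17 days later (15±2). The documents give no effect size, SD or within-subject correlation for training work, so the values below are assumptions in SD units. The only design calculation in the plan is for VO2max. With 20 per arm and SD 14, t(0.975, 38) × 14 × √(2/20) = 8.96, and scaling by √(χ²(0.90, 38)/38) gives 10.23, which agrees with the stated 10.3 or so. It is not used here.

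**Step 1: what the contrast estimates.** Let d5 be an arm's effect on work against cigarettes at V5 and dL the effect at a later visit.

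- Level contrast: dL
- Change-from-V5 contrast: dL − d5
- Level contrast with V5 as a covariate (equal SDs, correlation ρ): dL − ρ·d5

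**Step 2: numbers.**

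| d5 | dL | Level | Change from V5 | V5 as covariate, ρ = 0.5 / 0.7 / 0.9 |
|---|---|---|---|---|
| 0 | 0.5 | 0.50 | 0.50 | 0.50 / 0.50 / 0.50 |
| 0.5 | 0.5 | 0.50 | 0.00 | 0.25 / 0.15 / 0.05 |
| 0.5 | 0.8 | 0.80 | 0.30 | 0.55 / 0.45 / 0.35 |
| 0.8 | 0.5 | 0.50 | −0.30 | 0.10 / −0.06 / −0.22 |

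A simulation with 20 per arm and 20,000 replicates agreed with every entry to within 0.005. With no effect at V5 nothing is lost. A constant effect is lost entirely. A growing effect is understated by d5. A shrinking effect changes sign.

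**Step 3: precision.** With 20 per arm and SD 1, the standard error of an unadjusted level contrast is √(2/20) = 0.316. For change from V5 it is √(4(1 − ρ)/20), which is 0.316, 0.245 and 0.141 at ρ = 0.5, 0.7 and 0.9. Adjusting the level for a V3 measure with correlation r gives 0.316·√(1 − r²). This equals the change score when 1 − r² = 2(1 − ρ), that is r = √0.4 = 0.63 at ρ = 0.7 and r = √0.8 = 0.89 at ρ = 0.9. So at high ρ the change score can be the more precise, but it estimates a different quantity.

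**Step 4: where a V5 difference can be seen.** SAP 9.6.1.2.3 summarises work and work rate by arm at V5, V14, V29 and V41, with box plots, and SAP 9.1.2 gives a 95% CI on each arm mean. No adjusted difference between arms is planned at V5.

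**The case against.** The strongest reply is that progression is a legitimate target. The study title names trainability, and Protocol 4.2 expects carbon monoxide exposure to affect the response to training. Change from V5 estimates exactly that. This stands, and is why the change score should be kept. It does not answer the wider question of how much work each arm was able to do.

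Four further points have weight.

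- *The early effect is modelled elsewhere.* VO2max and exercise capacity at V4 have adjusted contrasts with 95% CIs. True, but neither is work done in training sessions.
- *V5 levels are not hidden.* Correct: a constant advantage would show in the descriptive tables and plots, although unadjusted.
- *Groups are formed by actual product use, so V5 corrects for unequal fitness.* A V3 measure can address that imbalance without removing the product effect.
- *Levels have their own problem.* Sessions run to heart-rate targets (Protocol 7.6.3), Protocol 2.1.1 says nicotine raises submaximal heart rate, and only the cigarette and IQOS arms are offered their product 30-60 minutes before a session. Work at a target heart rate may differ between arms for that reason alone. Change from V5 cancels any constant part of this offset. The point stands as a caution on interpretation; the SAP does not offer it as a rationale.

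A reader might also infer that the SAP breaks its own rule, "The baseline value for any given parameter will be the last assessment prior to randomization". The documents do not support that as a plain contradiction: no training session precedes randomisation, so the rule cannot be applied literally, and the SAP states a specific definition for this endpoint.

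**Conclusion.** The concern holds. The planned contrast is dL − d5, and any product effect on session work that is present at V5 is removed in full from the modelled result. This follows from the algebra and needs no assumption about variance. How much is lost depends on d5, which the documents do not give; the table shows the range from nothing to a reversed sign.

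Three stronger readings are tempting and are not supported:

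- That the product effect is complete by V5. Protocol 4.2 supports an effect before then, not a complete one.
- That the model is always biased toward no effect. That fits a constant or growing advantage; a shrinking one reverses sign, and an effect that starts after V5 is estimated without loss.
- That Protocol 12.5 has the same defect. It makes the level the endpoint and does not name V5 as the baseline. If V5 were used as the covariate, part of the effect would be removed rather than all of it when 0 < ρ < 1.

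The study is descriptive, with no hypothesis test, so the consequence is a misread estimate and not an error-rate problem.

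**What to change.** In SAP 9.6.1.1.3:

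1. Model the observed value at each session (work and work rate, absolute and per kg), with V5 included as a visit.
2. Adjust for a pre-randomisation fitness measure, either the highest wattage in the V3 VO2max test or V3 VO2max, and not for V5.
3. Report adjusted arm differences with 95% CIs at V5 and at the later programme-1 visits, V14, V29 and V41.
4. Keep change from V5 as a secondary analysis, labelled as progression after the first session.
5. List the change in SAP section 7.
6. State, for the level results, that sessions run to heart-rate targets and that arm differences in work may partly reflect nicotine's effect on heart rate.

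The cost is SAP wording and a changed MODEL statement. V3 wattage is already recorded because it sets the exercise capacity workload (Protocol 7.6.2). The downside is that the level contrast may be less precise than the change score if within-subject correlation is high. It is small because the change score is still reported.
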